#### 2.5.4 Pharmacokinetic (PK) and Pharmacodynamic (PD) studies

While the combination of decitabine and venetoclax has been studied and is currently being utilized clinically, adding nivolumab to this combination is novel. Venetoclax has low bioavailability, high inter-patient PK variability, and is susceptibility to drug-drug interactions (DDIs) through inhibition of intestinal CYP3A4, P-glycoprotein (P-gp), and BCRP and liver CYP3A4 and OATP1B1. Antifungal agents, which are routinely administered concurrently with venetoclax, are moderate-to-strong inhibitors of CYP3A4, and the drug transporters P-gp, BCRP, and OATP1B1. The unpredictable PK properties of venetoclax and high DDI potential warrant detailed plasma PK evaluation of venetoclax during AML therapy.

Plasma biomarker assays for OATP1B1 activity will also be incorporated to determine

OATP1B1 activity in relation to antifungal and venetoclax treatment (DOI: 10.1124/dmd.119.089474). As liver uptake by the transporters OATP1B1 can be a rate-limiting step to CYP3A4-mediated drug metabolism, and azoles and echinocandins are potent inhibitors of OATP1B1, we will also measure plasma biomarkers for OATP1B1 activity before and after administration antifungal/venetoclax. In order to assess the degree of OATP1B1 inhibition, analysis of glycochenodeoxycholate sulfate (GCDGA-S) and chenodeoxycholate-24-glucuronide (CDCA-24G) levels will be performed in plasma samples as validated surrogate endogenous substrates of OATP1B1/OATP1B3. Previous clinical studies have indicated that the AUC of GCDCA-S can be increased >20-fold following treatment with OATP1B1/3 inhibitors, whereas CDCA-24G is only detectable after the administration of OATP1B1/3 inhibitors. In addition to these bile acids, the co-proporphyrins CP-I and CP-III will be examined as OATP1B1/3 biomarkers. These compounds are known OATP1B1/3 substrates in vitro, and their plasma levels are significantly increased in Oatp1a/1b gene cluster knockout mice, compared with wild-type animals (up to 18.4-fold) as well as in humans receiving OATP1B1/3 inhibitors. The selectivity of CP-I and CP-III for OATP1B1 and OATP1B3 has been confirmed by the demonstration that these compounds are not transported by OCT1, OCT2, OAT3, or NTCP.

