Plasma venetoclax and serum nivolumab concentration-time profiles will be analyzed by non compartmental analysis in Phoenix Winonlin, and subsequently by population mixed effects PK modeling using NONMEM. Pharmacokinetic parameters (e.g., Cmax, AUC, CL, V, and t1/2) will be estimated. For venetoclax PK, concurrent antifungal medications will be grouped as strong (e.g., posaconazole, voriconazole) or moderate (e.g., fluconazole, isavuconazole) CYP3A4 inhibitors, or OATP1B1 inhibitors (e.g, micagungin) and included as a covariate in the venetoclax population PK model. Associations between: 1) antifungal drug administered and/or venetoclax exposure and changes in OATP1B1 plasma biomarkers from baseline to post-treatment; and 2) drug exposure parameters such as Cmax and AUC with toxicity or response will be performed using standard t-tests or Wilcoxon rank sum tests and illustrated using boxplots or other graphical displays. Values will be log transformed as appropriate to reflect biologic plausibility assessment.

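### For venetoclax exposure versus change in OATP1B1 biomarkers, section 9.3 names only two-group tests, which require an unstated cut of a continuous variable and cannot adjust for antifungal class.

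*Combined protocol and SAP*

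**What the plan says.** The relevant text is the last paragraph of section 9.3. It sets out two associations. The first is between "antifungal drug administered and/or venetoclax exposure and changes in OATP1B1 plasma biomarkers from baseline to post-treatment". The second is between "drug exposure parameters such as Cmax and AUC with toxicity or response". One clause covers both: they "will be performed using standard t-tests or Wilcoxon rank sum tests and illustrated using boxplots or other graphical displays". The paragraph allows log transformation. For the first association it names no correlation, no regression and no cut-point.

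The scales follow from the text. For exposure, "Pharmacokinetic parameters (e.g., Cmax, AUC, CL, V, and t1/2) will be estimated". For the biomarkers, section 2.5.4 lists GCDCA-S, CDCA-24G, CP-I and CP-III, all measured as plasma concentrations. Section 5.1 places the baseline sample before venetoclax and azole, and the later samples on Cycle 1 Day 14.

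For the population PK model, 9.3 says that "concurrent antifungal medications will be grouped as strong (e.g., posaconazole, voriconazole) or moderate (e.g., fluconazole, isavuconazole) CYP3A4 inhibitors, or OATP1B1 inhibitors" and enters that grouping as a covariate for venetoclax PK. It does not extend the covariate to the biomarker analysis.

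**The concern.** A t-test or rank-sum test compares two groups. It suits exposure against a yes/no toxicity or response. It does not suit exposure against biomarker change when both are measured on a continuous scale. To follow the text, the analyst must split one variable. Where to split is left open until the data are in hand, and the split discards information.

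The second difficulty is confounding. Section 2.5.4 describes azoles and echinocandins as potent OATP1B1 inhibitors, so antifungal choice can move the biomarkers directly. Section 6.4.1.1 sets the venetoclax dose according to the antifungal, and 2.5.4 expects antifungals to alter venetoclax PK, so the choice can also move exposure. A two-group test of high against low exposure cannot separate these routes. An apparent link between exposure and biomarker could be only the antifungal effect.

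**Working it through.** **The plan's own figures.** Section 9.3 gives no significance level, effect size or power for this analysis. The only error rates in the plan belong to the expansion-cohort rule in 9.1 (13 or more responses of 30; 30% against 50%). The exact binomial gives P(X ≥ 13 | 0.30) = 0.0845 and P(X ≤ 12 | 0.50) = 0.1808, matching the stated 0.084 and 0.181. That rule supplies only a plausible n of 30; section 9.2 gives the maximum, 42.

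**Assumptions (not in the documents).** Two-sided 5%; bivariate normal data after transformation; true correlation ρ from 0.2 to 0.8; complete PK and biomarker data in 18 to 42 patients; exposure split at the median unless stated.

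**Cost of the split in theory.** Splitting a normal variable at its median multiplies its correlation with any other variable by √(2/π) = 0.80. Relative efficiency is 2/π = 0.64. At ρ = 0.5 the split test therefore works with about 0.5 × 0.80 = 0.40.

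**Cost by simulation.** 20,000 trials per setting, n = 30; power in %, losses in points from unrounded figures:

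| ρ | Pearson | t-test after split | Loss | Spearman | Rank sum after split | Loss |
|---|---|---|---|---|---|---|
| 0.3 | 37.4 | 24.2 | 13.2 | 33.6 | 22.2 | 11.4 |
| 0.4 | 61.1 | 41.0 | 20.0 | 55.4 | 37.8 | 17.5 |
| 0.5 | 82.8 | 61.0 | 21.8 | 77.4 | 56.7 | 20.7 |
| 0.6 | 95.4 | 79.9 | 15.5 | 92.3 | 75.8 | 16.5 |

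The theory agrees: the split t-test at ρ = 0.5 (61.0%) performs like Pearson at ρ = 0.4 (61.1%). Over these rows the loss is about 11 to 22 points.

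**Outside that window** (t-test against Pearson):
- ρ = 0.2: loss of 3.0 points at n = 18, rising to 7.8 at n = 42.
- ρ = 0.6, n = 18: 24.6 points.
- ρ = 0.5, n = 42: 16.3 points (93.4% against 77.1%).
- ρ = 0.8: 0.8 points at n = 30 and 0.0 at n = 42.
- One-third/two-thirds split, n = 30, ρ = 0.5: 25.5 points.

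The whole grid runs from about 0 to 26 points.

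**Power of the class-adjusted model.** Take n = 30, ρ = 0.5, two equal antifungal classes that differ in mean exposure by d within-class SDs, and no direct class effect on the biomarker. Class then explains (d²/4)/(1 + d²/4) of exposure variance.
- d = 1: 0.25/1.25 = 20%. Adjusted regression has about 73% to 74% power against about 62% for the split t-test, a gain of about 11 points.
- d = 1.5: 0.5625/1.5625 = 36%. About 64% against 62% to 63%, essentially no gain.
- With four classes the adjusted power is lower: about 69% at d = 1 and 60% at d = 1.5.

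**False positives from confounding.** Take n = 30, two equal classes and no true exposure effect, with class shifting both variables:

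| Shift in exposure (SD) | Shift in biomarker (SD) | Split t-test rejects | Class-adjusted regression rejects |
|---|---|---|---|
| 0.5 | 0.5 | about 6% | about 5% |
| 0.5 | 1 | about 8% | about 5% |
| 1 | 1 | about 15% | about 5% |
| 1.5 | 1.5 | about 45% | about 5% |

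**CDCA-24G.** Section 2.5.4 says "CDCA-24G is only detectable after the administration of OATP1B1/3 inhibitors". The baseline sample precedes both venetoclax and azole, so the ratio of post-treatment to baseline may have no measurable denominator. For this marker a detected/not detected outcome may be natural, and a two-group test of exposure could then fit.

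**The case against.** The strongest reply is that little depends on this analysis. Section 5.6 labels it exploratory and gives its purpose as the effect of the antifungal agent, which is a group comparison. The wording of the first association makes exposure one option of an and/or. Objective 1.2.8 covers PK and PD generally and does not name OATP1B1. No dose, stopping or efficacy decision rests on the result. The three-class grouping is stated for the PK model only, and two-group tests remain valid for any two-class contrast. The plan's allowance for other graphical displays already permits scatter plots. All of this stands and sets the severity.

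It does not remove the mismatch. Section 2.5.4 states the aim as OATP1B1 activity in relation to both antifungal and venetoclax treatment, so the exposure half is intended. Section 9.3 keeps the T-cell and methylation work primarily descriptive but prescribes tests here; a prescribed test should fit its variables.

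Three stronger readings are tempting, and the documents do not support them.
- A reader might infer a fixed loss of some 10 to 20 points of power. The correlation, split rule, significance level and PK sample size are all unstated, and the loss can be close to nil.
- A reader might infer that class-adjusted regression recovers all the lost power and also removes confounding. In the 1.5 SD setting, where protection matters most, the power gain all but disappears.
- A reader might infer that serious confounding is established. The venetoclax doses in 6.4.1.1 are lowered because CYP3A inhibitors are given with them, so the net shift in exposure could be small, and with it the inflation. The possible rise in GCDCA-S of more than 20-fold cited in 2.5.4 also means that normal-theory figures are only indicative.

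**Conclusion.** The point holds for one exploratory pair: venetoclax exposure against change in the continuous OATP1B1 biomarkers. The named tests cannot be applied to it without a cut that the plan does not specify, and they cannot adjust for antifungal class.

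The size is conditional. The loss of about 11 to 22 points is against an unadjusted correlation and rests on n = 30, two-sided 5%, a median split, normality and ρ of 0.3 to 0.6. The better case for regression is validity rather than power, because it stays near 5% false positives whatever the class shifts. The tests named for exposure against binary toxicity or response are suitable. Severity is low.

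**What to change.** In section 9.3, for this pair only, replace the two-group tests as follows.
- For GCDCA-S, CP-I and CP-III: linear regression of the log of post-treatment over baseline on log venetoclax AUC or Cmax, kept continuous, with antifungal class as a factor (including a level for patients on none). Report the slope with its 95% confidence interval, and Spearman correlation as a check.
- For CDCA-24G: analyse detected/not detected, or use a rank method, since baseline may be undetectable.
- For antifungal class alone: an overall F or Kruskal-Wallis test when more than two classes are compared.
- Keep t-tests or rank-sum tests for genuine two-group comparisons, including exposure against binary toxicity or response.

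The cost is wording: no new samples, visits or patients. The downsides are a few degrees of freedom for class, which matter in a sample this small, and an assumed log-linear relation, which the Spearman check partly covers.

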## 10. ADVERSE EVENTS: LIST AND REPORTING REQUIREMENTS

Adverse event (AE) monitoring and reporting is a routine part of every clinical trial. The following list of AEs (Section 10.1) and the characteristics of an observed AE (Sections 10.2 and 10.3) will determine whether the event requires expedited reporting via the CTEP Adverse Event Reporting System (CTEP-AERS) **in addition** to routine reporting.

### 10.1 Comprehensive Adverse Events and Potential Risks List(s) (CAEPRs)

The Comprehensive Adverse Events and Potential Risks list (CAEPR) provides a single list of reported and/or potential adverse events (AE) associated with an agent using a uniform presentation of events by body system. In addition to the comprehensive list, a subset, the Specific Protocol Exceptions to Expedited Reporting (SPEER), appears in a separate column and is identified with bold and italicized text. This subset of AEs (SPEER) is a list of events that are protocol specific exceptions to expedited reporting to NCI (except as noted below). Refer to the 'CTEP, NCI Guidelines: Adverse Event Reporting Requirements' [http://ctep.cancer.gov/protocolDevelopment/electronic\\_applications/docs/aeguidelines.pdf](http://ctep.cancer.gov/protocolDevelopment/electronic_applications/docs/aeguidelines.pdf) for further clarification.

**NOTE:** Report AEs on the SPEER ONLY IF they exceed the grade noted in parentheses next to the AE in the SPEER. If this CAEPR is part of a combination protocol using multiple investigational agents and has an AE listed on different SPEERs, use the lower of the grades to determine if expedited reporting is required.

#### 10.1.1 CAEPR for Nivolumab

Version 2.4, December 2, 2020^1

Adverse Events with Possible Relationship to Nivolumab (CTCAE 5.0 Term) [n= 2069]			Specific Protocol Exceptions to Expedited Reporting (SPEER)
Likely (>20%)	Less Likely (<=20%)	Rare but Serious (<3%)	
BLOOD AND LYMPHATIC SYSTEM DISORDERS			
	Anemia		Anemia (Gr 3)
CARDIAC DISORDERS			

Adverse Events with Possible Relationship to Nivolumab (CTCAE 5.0 Term) [n= 2069]			Specific Protocol Exceptions to Expedited Reporting (SPEER)
Likely (>20%)	Less Likely (<=20%)	Rare but Serious (<3%)	
		Cardiac disorders - Other (cardiomyopathy)	
		Myocarditis	
		Pericardial tamponade 	
		Pericarditis	
ENDOCRINE DISORDERS			
	Adrenal insufficiency 		
	Hyperthyroidism 		
	Hypophysitis 		
	Hypothyroidism 		
EYE DISORDERS			
		Blurred vision	
		Dry eye	
		Eye disorders - Other (diplopia) 	
		Eye disorders - Other (Graves ophthalmopathy) 	
		Eye disorders - Other (optic neuritis retrobulbar) 	
		Eye disorders - Other (Vogt-Koyanagi-Harada)	
	Uveitis		
GASTROINTESTINAL DISORDERS			
	Abdominal pain		Abdominal pain (Gr 2)
	Colitis 		
		Colonic perforation 	
	Diarrhea		Diarrhea (Gr 3)
	Dry mouth		Dry mouth (Gr 2)
		Enterocolitis	
		Gastritis	
		Mucositis oral	
	Nausea		Nausea (Gr 2)
	Pancreatitis 		
GENERAL DISORDERS AND ADMINISTRATION SITE CONDITIONS			
Fatigue			Fatigue (Gr 3)
	Fever		Fever (Gr 2)
	Injection site reaction		Injection site reaction (Gr 2)
HEPATOBILIARY DISORDERS			
		Hepatobiliary disorders - Other (immune-mediated hepatitis)	
IMMUNE SYSTEM DISORDERS			
		Allergic reaction 	
		Autoimmune disorder 	
		Cytokine release syndrome 	
		Immune system disorders - Other (GVHD in the setting of allogeneic transplant) 	
		Immune system disorders - Other (sarcoidosis) 	
INJURY, POISONING AND PROCEDURAL COMPLICATIONS			
	Infusion related reaction 		

Adverse Events with Possible Relationship to Nivolumab (CTCAE 5.0 Term) [n= 2069]			Specific Protocol Exceptions to Expedited Reporting (SPEER)
Likely (>20%)	Less Likely (<=20%)	Rare but Serious (<3%)	
INVESTIGATIONS			
	Alanine aminotransferase increased 		Alanine aminotransferase increased (Gr 3)
	Aspartate aminotransferase increased 		Aspartate aminotransferase increased (Gr 3)
	Blood bilirubin increased 		Blood bilirubin increased (Gr 2)
	CD4 lymphocytes decreased		CD4 lymphocyte decreased (Gr 4)
	Creatinine increased		
	Lipase increased		
	Lymphocyte count decreased		Lymphocyte count decreased (Gr 4)
	Neutrophil count decreased		
	Platelet count decreased		
	Serum amylase increased		
METABOLISM AND NUTRITION DISORDERS			
	Anorexia		
		Hyperglycemia	Hyperglycemia (Gr 2)
		Metabolism and nutrition disorders - Other (diabetes mellitus with ketoacidosis) 	
MUSCULOSKELETAL AND CONNECTIVE TISSUE DISORDERS			
	Arthralgia		
		Musculoskeletal and connective tissue disorder - Other (polymyositis)	
		Myositis	
		Rhabdomyolysis	
NERVOUS SYSTEM DISORDERS			
		Encephalopathy 	
		Facial nerve disorder 	
		Guillain-Barre syndrome 	
		Myasthenia gravis 	
		Nervous system disorders - Other (demyelination myasthenic syndrome)	
		Nervous system disorders - Other (encephalitis) 	
		Nervous system disorders - Other (meningoencephalitis)	
		Nervous system disorders - Other (meningoradiculitis) 	
		Nervous system disorders - Other (myasthenic syndrome)	
		Peripheral motor neuropathy	
		Peripheral sensory neuropathy	
		Reversible posterior leukoencephalopathy syndrome 	
RENAL AND URINARY DISORDERS			
		Acute kidney injury 	
		Renal and urinary disorders - Other (immune-mediated nephritis)	

Adverse Events with Possible Relationship to Nivolumab (CTCAE 5.0 Term) [n= 2069]			Specific Protocol Exceptions to Expedited Reporting (SPEER)
Likely (>20%)	Less Likely (<=20%)	Rare but Serious (<3%)	
RESPIRATORY, THORACIC AND MEDIASTINAL DISORDERS			
	Pleural effusion 		
	Pneumonitis 		
		Respiratory, thoracic and mediastinal disorders - Other (bronchiolitis obliterans with organizing pneumonia) 	
SKIN AND SUBCUTANEOUS TISSUE DISORDERS			
		Erythema multiforme 	
	Pruritus 		Pruritus (Gr 2)
	Rash maculo-papular 		Rash maculo-papular (Gr 2)
		Skin and subcutaneous tissue disorders - Other (bullous pemphigoid)	
	Skin and subcutaneous tissue disorders - Other (Sweet's Syndrome) 		
	Skin hypopigmentation 		
		Stevens-Johnson syndrome	
		Toxic epidermal necrolysis	

This table will be updated as the toxicity profile of the agent is revised. Updates will be distributed to all Principal Investigators at the time of revision. The current version can be obtained by contacting [[contact]](mailto:[contact]). Your name, the name of the investigator, the protocol and the agent should be included in the e-mail.

Pericardial tamponade may be related to possible inflammatory reaction at tumor site.

 Nivolumab being a member of class of agents involved in the inhibition of “immune checkpoints”, may result in severe and possibly fatal immune-mediated adverse events probably due to T-cell activation and proliferation. This may result in autoimmune disorders that can include (but are not limited to) autoimmune hemolytic anemia, acquired anti-factor VIII immune response, autoimmune aseptic meningitis, autoimmune hepatitis, autoimmune nephritis, autoimmune neuropathy, autoimmune thyroiditis, bullous pemphigoid, exacerbation of Churg-Strauss Syndrome, drug rash with eosinophilia systemic symptoms [DRESS] syndrome, facial nerve disorder (facial nerve paralysis), limbic encephalitis, hepatic failure, pure red cell aplasia, pancreatitis, ulcerative and hemorrhagic colitis, endocrine disorders (e.g., autoimmune thyroiditis, hyperthyroidism, hypothyroidism, autoimmune hypophysitis/hypopituitarism, thyrotoxicosis, and adrenal insufficiency), sarcoid granuloma, myasthenia gravis, polymyositis, and Guillain-Barre syndrome.

Pancreatitis may result in increased serum amylase and/or more frequently lipase.

Cytokine release syndrome may manifest as hemophagocytic lymphohistiocytosis with accompanying fever and pancytopenia.

Complications including hyperacute graft-versus-host disease (GVHD), some fatal, have occurred in patients receiving allo stem cell transplant (SCT) after receiving Nivolumab. These complications may occur despite intervening therapy between receiving Nivolumab and allo-SCT.

Infusion reactions, including high-grade hypersensitivity reactions which have been observed following administration of nivolumab, may manifest as fever, chills, shakes, itching, rash, hypertension or hypotension, or difficulty breathing during and immediately after administration of nivolumab.

**Adverse events reported on Nivolumab trials, but for which there is insufficient evidence to suggest that there was a reasonable possibility that Nivolumab caused the adverse event:**

**BLOOD AND LYMPHATIC SYSTEM DISORDERS** - Leukocytosis

**CARDIAC DISORDERS** - Atrial fibrillation; Atrioventricular block complete; Heart failure; Ventricular arrhythmia

**EAR AND LABYRINTH DISORDERS** - Vestibular disorder

**EYE DISORDERS** - Eye disorders - Other (iritocyclitis); Optic nerve disorder; Periorbital edema

**GASTROINTESTINAL DISORDERS** - Constipation; Duodenal ulcer; Flatulence; Gastrointestinal disorders - Other (mouth sores); Vomiting

**GENERAL DISORDERS AND ADMINISTRATION SITE CONDITIONS** - Chills; Edema limbs; Malaise; Pain

**HEPATOBILIARY DISORDERS** - Bile duct stenosis

**IMMUNE SYSTEM DISORDERS** - Anaphylaxis; Immune system disorders - Other (autoimmune thrombotic microangiopathy); Immune system disorders - Other (limbic encephalitis)

**INFECTIONS AND INFESTATIONS** - Bronchial infection; Lung infection; Sepsis; Upper respiratory infection

**INVESTIGATIONS** - Blood lactate dehydrogenase increased; GGT increased; Investigations - Other (protein total decreased); Lymphocyte count increased; Weight loss

**METABOLISM AND NUTRITION DISORDERS** - Dehydration; Hyperuricemia; Hypoalbuminemia;

Hypocalcemia; Hyponatremia; Hypophosphatemia

**MUSCULOSKELETAL AND CONNECTIVE TISSUE DISORDERS** - Back pain; Musculoskeletal and connective tissue disorder - Other (musculoskeletal pain); Musculoskeletal and connective tissue disorder - Other (polymyalgia rheumatica); Myalgia; Pain in extremity

**NEOPLASMS BENIGN, MALIGNANT AND UNSPECIFIED (INCL CYSTS AND POLYPS)** - Neoplasms benign, malignant and unspecified (incl cysts and polyps) - Other (Histiocytic necrotizing lymphadenitis)

**NERVOUS SYSTEM DISORDERS** - Dizziness; Headache; Intracranial hemorrhage

**PSYCHIATRIC DISORDERS** - Insomnia

**RENAL AND URINARY DISORDERS** - Hematuria; Renal and urinary disorders - Other (tubulointerstitial nephritis)

**RESPIRATORY, THORACIC AND MEDIASTINAL DISORDERS** - Bronchospasm; Cough; Dyspnea; Hypoxia

**SKIN AND SUBCUTANEOUS TISSUE DISORDERS** - Alopecia; Dry skin; Hyperhidrosis; Pain of skin; Photosensitivity; Rash acneiform; Skin and subcutaneous tissue disorders - Other (rosacea)

**VASCULAR DISORDERS** - Flushing; Hypertension; Hypotension; Vasculitis

**Note:** Nivolumab in combination with other agents could cause an exacerbation of any adverse event currently known to be caused by the other agent, or the combination may result in events never previously associated with either agent.

#### 10.1.1.1 CAEPR for decitabine

Version 2.5, March 28, 2019

Adverse Events with Possible Relationship to Decitabine (5-aza-2'-deoxycytidine) (CTCAE 5.0 Term) [n= 1832]		
Likely (>20%)	Less Likely (<=20%)	Rare but Serious (<3%)
BLOOD AND LYMPHATIC SYSTEM DISORDERS		
Anemia		
	Febrile neutropenia	
GASTROINTESTINAL DISORDERS		
	Abdominal pain	
	Anal mucositis	

	Constipation		
	Diarrhea		
	Mucositis oral		
Nausea			
	Rectal mucositis		
	Small intestinal mucositis		
	Vomiting		
GENERAL DISORDERS AND ADMINISTRATION SITE CONDITIONS			
	Chills		
	Edema limbs		
Fatigue			
Fever			
	Non-cardiac chest pain		
	Pain		
IMMUNE SYSTEM DISORDERS			
	Autoimmune disorder		
INFECTIONS AND INFESTATIONS			
Infection 			
INJURY, POISONING AND PROCEDURAL COMPLICATIONS			
	Bruising		
INVESTIGATIONS			
	Alanine aminotransferase increased		
	Aspartate aminotransferase increased		
	Blood bilirubin increased		

Adverse Events with Possible Relationship to Decitabine (5-aza-2'-deoxycytidine) (CTCAE 5.0 Term) [n= 1832]		
Likely (>20%)	Less Likely (<=20%)	Rare but Serious (<3%)
	Creatinine increased	
	Lymphocyte count decreased	
Neutrophil count decreased		
Platelet count decreased		
White blood cell decreased		
METABOLISM AND NUTRITION DISORDERS		
	Anorexia	
	Hyperglycemia	
	Hyperuricemia	
	Hypoalbuminemia	
	Hypocalcemia	
	Hypokalemia	
	Hypomagnesemia	
	Hyponatremia	
MUSCULOSKELETAL AND CONNECTIVE TISSUE DISORDERS		
	Arthralgia	
	Back pain	
	Bone pain	
	Pain in extremity	
NERVOUS SYSTEM DISORDERS		
	Dizziness	
	Headache	
		Intracranial hemorrhage
	Somnolence	
PSYCHIATRIC DISORDERS		
	Anxiety	
	Insomnia	
RESPIRATORY, THORACIC AND MEDIASTINAL DISORDERS		
	Cough	
	Dyspnea	
	Laryngeal mucositis	
	Pharyngeal mucositis	
	Pharyngolaryngeal pain	
	Respiratory hemorrhage 	
	Tracheal mucositis	
SKIN AND SUBCUTANEOUS TISSUE DISORDERS		
	Alopecia	
	Pruritus	
	Purpura	
	Rash maculo-papular	
VASCULAR DISORDERS		
	Hematoma	
	Phlebitis	
	Vascular disorders - Other (hemorrhage with decreased platelets)	

This table will be updated as the toxicity profile of the agent is revised. Updates will be distributed to all Principal Investigators at the time of revision. The current version can be obtained by contacting [[contact]](mailto:[contact]). Your name, the name of the investigator, the protocol and the agent should be included in the e-mail.

Infection includes all 75 sites of infection under the INFECTIONS AND INFESTATIONS SOC.

Respiratory hemorrhage includes Bronchopulmonary hemorrhage, Epistaxis, Laryngeal hemorrhage, Mediastinal hemorrhage, Pharyngeal hemorrhage, and Pleural hemorrhage under the RESPIRATORY, THORACIC, AND MEDIASTINAL DISORDERS SOC.

Gastrointestinal hemorrhage includes Anal hemorrhage, Cecal hemorrhage, Colonic hemorrhage, Duodenal hemorrhage, Esophageal hemorrhage, Esophageal varices hemorrhage, Gastric hemorrhage, Hemorrhoidal hemorrhage, Ileal hemorrhage, Intra-abdominal hemorrhage, Jejunal hemorrhage, Lower gastrointestinal hemorrhage, Oral hemorrhage, Pancreatic hemorrhage, Rectal hemorrhage, Retroperitoneal hemorrhage, and Upper gastrointestinal hemorrhage under the GASTROINTESTINAL DISORDERS SOC.

Gastrointestinal obstruction includes Colonic obstruction, Duodenal obstruction, Esophageal obstruction, Ileal obstruction, Jejunal obstruction, Obstruction gastric, Rectal obstruction, and Small intestinal obstruction under the GASTROINTESTINAL DISORDERS SOC.

**Adverse events reported on decitabine (5-aza-2'-deoxycytidine) trials, but for which there is insufficient evidence to suggest that there was a reasonable possibility that decitabine (5-aza-2'-deoxycytidine) caused the adverse event:**

**BLOOD AND LYMPHATIC SYSTEM DISORDERS** - Blood and lymphatic system disorders - Other (coagulopathy); Blood and lymphatic system disorders - Other (lymphadenopathy); Blood and lymphatic system disorders - Other (pancytopenia); Blood and lymphatic system disorders - Other (spleen disorder); Bone marrow hypocellular; Eosinophilia; Hemolysis; Leukocytosis

**CARDIAC DISORDERS** - Atrial fibrillation; Atrial flutter; Atrioventricular block complete; Cardiac arrest; Cardiac disorders - Other (cardiac murmur); Cardiac disorders - Other (dilation atrial); Chest pain - cardiac; Heart failure; Myocardial infarction; Restrictive cardiomyopathy; Sinus bradycardia; Sinus tachycardia; Supraventricular tachycardia; Ventricular arrhythmia

**EAR AND LABYRINTH DISORDERS** - Ear pain; Vertigo

**EYE DISORDERS** - Blurred vision; Eye disorders - Other (eye hemorrhage); Eye disorders - Other (eye swelling); Eye pain

**GASTROINTESTINAL DISORDERS** - Abdominal distension; Anal fissure; Ascites; Dyspepsia; Dysphagia; Enterocolitis; Esophagitis; Flatulence; Gastritis; Gastroesophageal reflux disease; Gastrointestinal disorders - Other (diverticulitis); Gastrointestinal disorders - Other (mouth ulceration); Gastrointestinal disorders - Other (oral mucosal blistering); Gastrointestinal hemorrhage; Gastrointestinal obstruction; Gastrointestinal pain; Hemorrhoids; Ileus; Oral pain; Periodontal disease; Proctitis; Rectal pain; Toothache; Typhlitis

**GENERAL DISORDERS AND ADMINISTRATION SITE CONDITIONS** - Edema face; Gait disturbance; Injection site reaction; Localized edema; Malaise; Multi-organ failure

**HEPATOBILIARY DISORDERS** - Cholecystitis; Hepatic failure; Hepatobiliary disorders - Other (cholestasis); Hepatobiliary disorders - Other (hepatomegaly)

**IMMUNE SYSTEM DISORDERS** - Allergic reaction

**INJURY, POISONING AND PROCEDURAL COMPLICATIONS** - Fall; Fracture; Infusion related reaction; Injury, poisoning and procedural complications - Other (catheter site pain); Injury, poisoning and procedural complications - Other (hernia); Injury, poisoning and procedural complications - Other (procedural pain); Injury, poisoning and procedural complications - Other (stent occlusion)

**INVESTIGATIONS** - Activated partial thromboplastin time prolonged; Alkaline phosphatase increased; Blood bicarbonate decreased; Blood lactate dehydrogenase increased; CPK increased; Cardiac troponin I increased; Ejection fraction decreased; Electrocardiogram QT corrected interval prolonged; Fibrinogen decreased; GGT increased; INR increased; Investigations - Other (blood bicarbonate increased); Investigations - Other (blood bilirubin decreased); Investigations - Other (blood chloride decreased); Investigations - Other (blood chloride increased); Investigations - Other (blood urea increased); Investigations - Other (elevated ammonia); Investigations - Other (platelet count increased); Investigations - Other (protein total decreased); Lipase increased; Serum amylase increased; Weight loss

**METABOLISM AND NUTRITION DISORDERS** - Acidosis; Dehydration; Hypercalcemia; Hyperkalemia; Hypermagnesemia; Hyperphosphatemia; Hypoglycemia; Hypophosphatemia; Metabolism and nutrition disorders - Other (malnutrition)

**MUSCULOSKELETAL AND CONNECTIVE TISSUE DISORDERS** - Chest wall pain; Generalized muscle weakness; Muscle cramp; Myalgia

**NEOPLASMS BENIGN, MALIGNANT AND UNSPECIFIED (INCL CYSTS AND POLYPS)** - Leukemia secondary to oncology chemotherapy; Tumor pain

**NERVOUS SYSTEM DISORDERS** - Amnesia; Aphonia; Ataxia; Cognitive disturbance; Dysesthesia; Dysgeusia; Ischemia cerebrovascular; Lethargy; Paresthesia; Peripheral sensory neuropathy; Seizure; Stroke; Syncope; Transient ischemic attacks

**PSYCHIATRIC DISORDERS** - Confusion; Delirium; Depression; Personality change

**RENAL AND URINARY DISORDERS** - Acute kidney injury; Cystitis noninfective; Hematuria; Urinary fistula; Urinary frequency; Urinary retention; Urinary tract pain; Urinary urgency

**REPRODUCTIVE SYSTEM AND BREAST disorders** - Breast pain; Uterine hemorrhage; Vaginal hemorrhage

**RESPIRATORY, THORACIC AND MEDIASTINAL DISORDERS** - Adult respiratory distress syndrome; Allergic rhinitis; Atelectasis; Bronchospasm; Hypoxia; Nasal congestion; Pleural effusion; Pneumonitis; Postnasal drip; Pulmonary edema; Respiratory failure; Respiratory, thoracic and mediastinal disorders - Other (breath sounds abnormal /decreased); Respiratory, thoracic and mediastinal disorders - Other (crepitations); Respiratory, thoracic and mediastinal disorders - Other (pulmonary congestion); Sinus disorder; Wheezing

**SKIN AND SUBCUTANEOUS TISSUE DISORDERS** - Bullous dermatitis; Dry skin; Erythema multiforme; Hyperhidrosis; Hyperkeratosis; Skin and subcutaneous tissue disorders - Other (Sweet's syndrome); Skin hyperpigmentation; Skin hypopigmentation; Skin ulceration; Stevens-Johnson syndrome; Urticaria

**VASCULAR DISORDERS** - Flushing; Hypertension; Hypotension; Thromboembolic event; Vascular disorders - Other (aortic aneurysm); Vascular disorders - Other (catheter site hemorrhage); Vascular disorders - Other (circulatory collapse); Vascular disorders - Other (hemorrhage); Vascular disorders - Other (splenic infarct vs hemorrhage/rupture); Vascular disorders - Other (veno-occlusive disease); Vasculitis

**Note:** Decitabine (5-aza-2'-deoxycytidine) in combination with other agents could cause an exacerbation of any adverse event currently known to be caused by the other agent, or the combination may result in events never previously associated with either agent.

